**Table 9 (Cont.) - Clinical response: RECIST criteria – ITT population**

	Total (n=xx)	
	Visit xx	End of study treatment
New lesions, n (%)		
Yes		
No		
Total		
Overall response, n(%)		
Complete response		
Partial response		
Stable disease		
Progressive disease		
Inevaluable		
Total		

**Table 10 – Best overall response: RECIST criteria – ITT population**

	Total (n=xx)
Best overall response, n(%)	
Complete response	
Partial response	
Stable disease	
Progressive disease	
Inevaluable	
Total	
Objective response ratea), n (%), 95% CI	

a) Objective response rate: patients with complete or partial response.  
95% CI: 95% confidence interval.

**Table 11 – Best overall response: RECIST criteria – PP population**

	Total (n=xx)
Best overall response, n(%)	
Complete response	
Partial response	
Stable disease	
Progressive disease	
Inevaluable	
Total	
Objective response ratea), n (%), 95% CI	

a) Objective response rate: patients with complete or partial response.  
95% CI: 95% confidence interval.

**Table 12** – Progression free survival – ITT population

	Statistics	CI95%
PFS (weeks)		
N		
Censored		
Events (disease progression or death)		
Mean		
Median		
Percentile 25%		
Percentile 75%		
Minimum		
Maximum		

PFS: Progression free survival.

CI95%: 95% confidence interval.

**Table 13** – Progression free survival – PP population

	Statistics	CI95%
PFS (weeks)		
N		
Censored		
Events (disease progression or death)		
Mean		
Median		
Percentile 25%		
Percentile 75%		
Minimum		
Maximum		

PFS: Progression free survival.

CI95%: 95% confidence interval.

**Table 14 – Overall survival – ITT population**

	Statistics	CI95%
Overall survival (weeks)		
N		
Censored		
Events (death)		
Mean		
Median		
Percentile 25%		
Percentile 75%		
Minimum		
Maximum		

CI95%: 95% confidence interval.

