### **5.3.9.2 Secondary Efficacy Endpoints**

The secondary efficacy variables include:

- Progression-free survival (PFS), defined as the time from baseline visit to the date of first occurrence of disease progression or death for any cause while the patient was under study or during the prolonged follow-up period. PFS will be summarized as median time and will be estimated using the Kaplan-Meier method. Ninety five percent (95%) confidence interval will be estimated for median time to PFS.
  
- Overall survival (OS), defined as the time from the first dose of erlotinib to the date of death due to any cause while the patient was under study or during the prolonged follow-up period. Overall survival variable will be summarized as median time to OS and will be estimated using the Kaplan-Meier method. 95% confidence interval will be estimated for median time to OS. The date of first dose is not captured in the study CRF. Therefore, for this endpoint it will be assumed that the patient will take the first dose at the day of the baseline visit.
  
- Epidermal growth factor receptor (EGFR) mutation frequency. The presence of EGFR mutation (exon 19 deletion and/or exon 21 substitution L858R) in the study population will be presented as the relative frequency of those mutations among the total screened patients. A 95% confidence interval will be estimated for this value using binomial distribution.
  
- Response duration, defined as the time of initial response (CR/PR whichever is first recorded) until documented tumor progression. Response duration will be summarized as median time and will be estimated using the Kaplan-Meier method. Ninety five percent (95%) confidence interval will be estimated for median time to response duration.

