### Treatment period

**Response duration:** It will be measured from the time of initial response (CR/PR whichever is first recorded) until documented tumor progression (in weeks).

**Best overall response:** a categorical variable will be obtained, defined as the best response across all time points, according to RECIST 1.1, until end of study treatment. The following criteria will be considered:

Complete response – Patients who presented at least one complete response;

Partial response – Patients who not presented a complete response and presented at least one partial response;

Stable disease – Patients who not presented response (complete or partial) and presented at least one stable disease;

Progression disease – Patients who not presented response or stable disease and presented progression disease;

Inevaluable – All assessments are inevaluable.

**Objective response:** A dichotomous variable (yes/no) will be calculated. Patients who presented complete response or partial response as the best overall response will be classified in “yes”. Otherwise patients will be classified in “no”.

**Event PFS:** A dichotomous variable (yes/no) will be calculated. Patients who presented progression disease or death for any cause will be classified in “yes”. Otherwise patients will be classified in “no”.

**Time PFS:** Time between baseline visit and date of first occurrence of disease progression or death for any cause (in weeks) while the patient was under study or during the prolonged follow-up period. In patients where disease progression or death from any cause was not observed, the time will be censored at the date of last visit or last contact with the patient.

**Time overall survival:** The time from the first dose of erlotinib (assumed to be baseline visit) to the date of death due to any cause (in weeks). For patients alive at the end of the follow-up period, the time was censored at the date of last visit or last contact with the patient.

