**Table 18 – Response duration– ITT population**

	Statistics	CI95%
Response duration (weeks)		
N		
Censored		
Events (death)		
Mean		
Median		
Percentile 25%		
Percentile 75%		
Minimum		
Maximum		

CI95%: 95% confidence interval.

**Table 19** – Response duration– PP population

	Statistics	CI95%
Response duration (weeks)		
N		
Censored		
Events (death)		
Mean		
Median		
Percentile 25%		
Percentile 75%		
Minimum		
Maximum		

CI95%: 95% confidence interval.

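### The survival table shells carry an undefined Mean row for censored PFS, OS and response duration; at the interim cut-off it would be a truncated mean set by follow-up

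*SAP*

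**What the plan says.** SAP 5.3.9.2 is clear about OS: "Overall survival variable will be summarized as median time to OS and will be estimated using the Kaplan-Meier method", and "95% confidence interval will be estimated for median time to OS". PFS and response duration get the same treatment. A mean is mentioned for none of the three.

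SAP Appendix 3 right-censors both survival endpoints. For patients still alive, OS is handled so that "the time was censored at the date of last visit or last contact with the patient"; for patients without progression or death, PFS is handled so that "the time will be censored at the date of last visit or last contact with the patient". Appendix 3 gives no censoring rule for response duration, although its tables have a Censored row.

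The shells in SAP Appendix 6 ("Progression free survival – ITT population", "Table 14 – Overall survival – ITT population", "Response duration– ITT population", their per-protocol twins, and PFS by exon) share one layout: N, Censored, Events, Mean, Median, two percentiles, Minimum, Maximum. A single column headed as the 95% CI runs beside every row.

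SAP 6.12 applies the whole of section 6.9, and so these tables, to the interim analysis. SAP 5.5 names PFS and OS for the interim but not response duration. The cut-off of 30 September 2013 (Protocol 8.2.7, SAP 3.4) is the only dated one; the end of the study has no calendar date (Protocol 3.1).

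**The concern.** Text and tables disagree on what is reported, and the extra row asks for something the data will usually not support. The mean of a survival time is the area under the whole survival curve. If the longest observed time is censored, the curve has not reached zero and the rest of the area is unknown. What can be computed is the area up to some stopping point. Unless that point is fixed in advance, it is set by when patients entered, when the data were cut and which patient happened to be last.

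Such a figure understates the mean, rises at each later cut with no change in the patients, and can sit below the median printed in the next row. Protocol 3.3 says the interim is meant to be compared with published results, so an unlabelled mean invites a wrong reading.

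**Working it through.** The documents state no mean survival time, so there is no plan figure to reproduce. The check asks what the row would contain at the interim.

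**Inputs from the documents**
- n = 30 (Protocol 8.2.6).
- Recruitment ends by end March 2012 (Protocol 4.4); cut-off 30 September 2013. That is 548 days, or 548/7 = 78.3 weeks (18.0 months), the minimum potential follow-up.
- Median PFS on first-line erlotinib: 12.5 months in the pooled analysis and 14.0 months in the Spanish study (Protocol 1.3).

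**Assumptions**
- Recruitment length (its start is not given): 9 or 15 months, with 6 to 18 months as a wider range.
- OS median 18 to 30 months; the documents give none for this population and treatment.
- Exponential times, with Weibull shape 1.4 as a check; follow-up complete to the cut-off.

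**Formulas.** For an exponential curve with median m, the true mean is m/ln 2. The mean restricted to horizon τ is (m/ln 2)(1 − 2^(−τ/m)).
- PFS, m = 12.5 months, τ = 18: 18.0 × (1 − 2^(−1.44)) = 18.0 × 0.631 = 11.4 months, against a true mean of 18.0.
- The restricted mean is below the median when 2^(−τ/m) > 1 − ln 2 = 0.307, that is when τ < 1.70 m. The limit is 21.3 months for m = 12.5, and 30.7, 40.9 and 51.1 months for m = 18, 24 and 30.
- With 9 or 15 months of recruitment no patient can be followed beyond 27 or 33 months. For OS medians of 24 and 30 months the limit is out of reach.

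**Simulation** (3000 trials per setting, exponential times, Kaplan-Meier area to the last event, recruitment over 9 and 15 months)

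| Endpoint | Median, months (weeks) | True mean, weeks | Average table mean, weeks |
|---|---|---|---|
| PFS | 12.5 (54) | 78 | 55 and 59 |
| OS, assumed | 18 (78) | 113 | 64 and 71 |
| OS, assumed | 24 (104) | 151 | 70 and 78 |
| OS, assumed | 30 (130) | 188 | 73 and 83 |

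Stopping at the last observed time instead of the last event raises the OS figure for a 24-month median only to 80 and 91 weeks.

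**How often is the longest time censored?** With 6 to 18 months of recruitment: 86% to 98% of trials for PFS (medians 12.5 to 14.0) and 93% to 99% for OS. With Weibull shape 1.4: 67% to 94% and 85% to 99%.

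**How often does the mean fall below the same trial's Kaplan-Meier median, where that median is reached?**

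| Endpoint (median, months) | Area to last event | Area to last observation |
|---|---|---|
| PFS (12.5 to 14.0) | 18% to 61% | 5% to 40% |
| OS (18) | 54% to 85% | 28% to 66% |
| OS (24) | 82% to 96% | 58% to 85% |
| OS (30) | 93% to 98% | 76% to 91% |

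**Shape of the PFS curve.** For a 12.5-month median the exponential shortfall, with the area taken to the last event, is 25% to 30%. With Weibull shape 1.4 the true mean is 64 weeks and the shortfall 9% to 13% (5% to 9% to the last observation).

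**Later cut.** With at least 60 months of follow-up, the mean falls below the median in about 0% to 1% of trials for PFS, 4% to 9% for a 24-month OS median and 11% to 20% for a 30-month one.

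Response duration is not sized here: the documents give neither a median nor a censoring rule for it.

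**The case against.** The strongest reply is that nothing depends on this row. The median is the planned summary, the cited first-line PFS benchmarks are medians, there is no hypothesis test (Protocol 8.2.2), and the Censored row warns the reader. All of that stands, and it limits the point to a reporting correction.

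Four stronger readings are tempting, and the documents do not support them:
- **That the trial's PFS and OS results would be biased low.** Only the Mean row is affected; the Kaplan-Meier median and its CI are not.
- **That the SAP plans a 95% CI for the mean.** The column is blank and also stands beside N and Censored. The text plans an interval for the median only.
- **That the mean falls well below the median for every endpoint.** For PFS the average table mean of 55 to 59 weeks is at or slightly above the 54-week median. The large gaps are for OS and rest on assumed medians. For a 24-month OS median the table's own median is not reached in 20% to 42% of trials, so the two rows cannot always be compared.
- **That the final analysis is equally affected.** The figures above are for the interim; longer follow-up largely removes the effect for PFS and reduces it for OS.

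The SAP also does not say which mean is meant. The general rule in 5.3 gives a mean for continuous variables, so a plain average of observed times is possible. That too is limited by follow-up: it fell below the median in 19% to 55% of simulated PFS trials. The ambiguity is a reason to define or remove the row.

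One consideration runs the other way. OS is censored at last contact, and survival contact is only about every 6 months (Protocol 5.6), so actual follow-up at the cut-off may be shorter than simulated.

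**Conclusion.** The point holds as a correction to the table shells. Eight tables ask for a mean that the text neither plans nor defines, and at the interim the value would in most cases be truncated by follow-up.

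The size is large for OS (roughly 40% to 60% below the exponential true mean: 1 − 71/113 = 37% to 1 − 73/188 = 61%) and modest for PFS (about 10% to 30%). The OS figures depend on assumed medians and on an exponential tail. At shape 1.4 the true mean is 64/54.4 = 1.18 times the median, not 1/ln 2 = 1.44 times, so a 24-month median implies about 123 weeks and not 151. The conclusion that an unrestricted mean is usually not estimable at the interim holds under both shapes. No planned inference changes.

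**What to change.** Delete the Mean row from SAP Tables 12-15 and 18-21, which brings them into line with 5.3.9.2. If a mean is wanted, replace the row with a restricted mean labelled as such, and state its horizon and CI method in 5.3.9.2 before the data are cut. State also which rows the CI column applies to.

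Minimum and Maximum may stay if censored values are flagged. As an optional addition, report Kaplan-Meier percentages with 95% CIs at fixed times that actual follow-up supports, such as 26 and 52 weeks. Seventy-eight weeks is open to question because it equals the whole minimum interval to the cut-off, while OS censoring falls at the last contact.

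The cost is a shell edit and, if a restricted mean is kept, a sentence or two of text. No new data are needed.

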**Table 15 – Overall survival – PP population**

	Statistics	CI95%
Overall survival (weeks)		
N		
Censored		
Events (death)		
Mean		
Median		
Percentile 25%		
Percentile 75%		
Minimum		
Maximum		

CI95%: 95% confidence interval.

**Table 16 – Epidermal growth factor receptor – All patients**

	Total (n=xx)
EGFR test performed, n(%)	
Yes	
No	
Total	
EGFR positive result, n (%), 95% CI	
Positive	
Negative	
Total	
Exon 19 and/or exon 21 mutations, n (%)	
Exon 19	
Exon 21	

Positive result: patients with Exon 19 and/or exon 21 mutations.

**Table 17 – Epidermal growth factor receptor**

	Total (n=xx)
Exon 19 and/or exon 21 mutations, n (%)	
ITT Population	
Exon 19	
Exon 21	
PP Population	
Exon 19	
Exon 21	

Positive result: patients with Exon 19 and/or exon 21 mutations.

**Table 18 – Response duration– ITT population**

	Statistics	CI95%
Response duration (weeks)		
N		
Censored		
Events (death)		
Mean		
Median		
Percentile 25%		
Percentile 75%		
Minimum		
Maximum		

CI95%: 95% confidence interval.

**Table 19** – Response duration– PP population

	Statistics	CI95%
Response duration (weeks)		
N		
Censored		
Events (death)		
Mean		
Median		
Percentile 25%		
Percentile 75%		
Minimum		
Maximum		

CI95%: 95% confidence interval.

**Table 20 – Progression free survival by exon 19 and 21– ITT population**

	Exon 19		Exon 21	
	Statistics	CI 95%	Statistics	CI 95%
PFS (weeks)				
N				
Censored				
Events (disease progression or				
Mean				
Median				
Percentile 25%				
Percentile 75%				
Minimum				
Maximum				

PFS: Progression free survival.

CI95%: 95% confidence interval.

**Table 21** – Progression free survival by exon 19 and 21– PP population

	Exon 19		Exon 21	
	Statistics	CI 95%	Statistics	CI 95%
PFS (weeks)				
N				
Censored				
Events (disease progression or				
Mean				
Median				
Percentile 25%				
Percentile 75%				
Minimum				
Maximum				

PFS: Progression free survival.

CI95%: 95% confidence interval.

**Table 22 – Drug dispensing and accountability – Safety population**

	Total (n=xx)
Starting dose of study drug, n (%)	
150 mg	
100 mg	
50 mg	
Total	
Reduction in starting dose, n (%)	
Yes	
No	
Total	
Dose per day (mg)	
N	
Mean	
Median	
Standard Deviation	
Minimum	
Maximum	
Cumulative dose (mg)	
N	
Mean	
Median	
Standard Deviation	
Minimum	
Maximum	
Duration of study drug dispensability (weeks)	
N	
Mean	
Median	
Standard Deviation	
Minimum	
Maximum	
Study drug dispensed (tablets)	
N	
Mean	
Median	
Standard Deviation	
Minimum	
Maximum	
Study drug used (tablets)	
N	
Mean	
Median	
Standard Deviation	
Minimum	
Maximum	
Study drug unused (tablets)	
N	
Mean	
Median	
Standard Deviation	
Minimum	
Maximum	

**Table 22 (Cont.) – Drug dispensing and accountability – Safety population**

	Total (n=xx)
Study drug missing (tablets)	
N	
Mean	
Median	
Standard Deviation	
Minimum	
Maximum	
Drug compliance (%)	
N	
Mean	
Median	
Standard Deviation	
Minimum	
Maximum	
Patient compliant, n (%)	
Yes	
No	
Total	

**Table 23 – Physical examination – Safety population**

	Total (n=xx)					
		Screening	Baseline	Visit xx	End of study treatment	End of study
Physical examination performed, n (%)						
Yes						
No						
Total						
Skin examination, n (%)						
Normal						
Abnormal						
Total						
Nails examination, n(%)						
Normal						
Abnormal						
Total						
Thorax examination, n(%)						
Normal						
Abnormal						
Total						
Abdomen examination, n(%)						
Normal						
Abnormal						
Total						
Extremities examination, n(%)						
Normal						
Abnormal						
Total						
Head examination, n(%)						
Normal						
Abnormal						
Total						
Genital examination, n(%)						
Normal						
Abnormal						
Total						
Neurologic examination, n(%)						
Normal						
Abnormal						
Total						
Temperature examination, n(%)						
Normal						
Abnormal						
Total						
Other physical examination, n(%)						
Yes						
No						
Total						

**Table 24 – Electrocardiogram – Safety population**

	Total (n=xx)				
	Screening	Baseline	Visit xx	End of study treatment	End of study
ECG performed, n (%)					
Yes					
No					
Total					
ECG result, n (%)					
Normal					
Abnormal, clinically irrelevant					
Abnormal, clinically relevant					
Total					

ECG: Electrocardiogram.

**Table 25 – Hematology – Safety population**

	Total (n=xx)				
	Screening	Baseline	Visit xx	End of study treatment	End of study
Hemoglobin, n (%)					
Normal					
Abnormal, clinically irrelevant					
Abnormal, clinically relevant					
Total					
Baseline versus current visit					
Normal - Normal	-	-	-	-	-
Normal - Abnormal, clinically irrelevant	-	-	-	-	-
Normal - Abnormal, clinically relevant	-	-	-	-	-
Abnormal, clinically irrelevant - Normal	-	-	-	-	-
Abnormal, clinically irrelevant - Abnormal, clinically irrelevant	-	-	-	-	-
Abnormal, clinically irrelevant - Abnormal, clinically relevant	-	-	-	-	-
Abnormal, clinically relevant - Normal	-	-	-	-	-
Abnormal, clinically relevant - Abnormal, clinically relevant	-	-	-	-	-
Abnormal, clinically relevant - Abnormal, clinically irrelevant	-	-	-	-	-
Leucocytes, n (%)					
Normal					
Abnormal, clinically irrelevant					
Abnormal, clinically relevant					
Total					
Baseline versus current visit					
Normal - Normal	-	-	-	-	-
Normal - Abnormal, clinically irrelevant	-	-	-	-	-
Normal - Abnormal, clinically relevant	-	-	-	-	-
Abnormal, clinically irrelevant - Normal	-	-	-	-	-
Abnormal, clinically irrelevant - Abnormal, clinically irrelevant	-	-	-	-	-
Abnormal, clinically irrelevant - Abnormal, clinically relevant	-	-	-	-	-
Abnormal, clinically relevant - Normal	-	-	-	-	-
Abnormal, clinically relevant - Abnormal, clinically relevant	-	-	-	-	-
Abnormal, clinically relevant - Abnormal, clinically irrelevant	-	-	-	-	-

**Table 25 (Cont.) – Hematology – Safety population**

	Total (n=xx)				
	Screening	Baseline	Visit xx	End of study treatment	End of study
Neutrophils, n (%)					
Normal					
Abnormal, clinically irrelevant					
Abnormal, clinically relevant					
Total					
Baseline versus current visit					
Normal - Normal	-	-	-	-	-
Normal - Abnormal, clinically irrelevant	-	-	-	-	-
Normal - Abnormal, clinically relevant	-	-	-	-	-
Abnormal, clinically irrelevant - Normal	-	-	-	-	-
Abnormal, clinically irrelevant - Abnormal, clinically irrelevant	-	-	-	-	-
Abnormal, clinically irrelevant - Abnormal, clinically relevant	-	-	-	-	-
Abnormal, clinically relevant - Normal	-	-	-	-	-
Abnormal, clinically relevant - Abnormal, clinically relevant	-	-	-	-	-
Abnormal, clinically relevant - Abnormal, clinically irrelevant	-	-	-	-	-
Platelets, n (%)					
Normal					
Abnormal, clinically irrelevant					
Abnormal, clinically relevant					
Total					
Baseline versus current visit					
Normal - Normal	-	-	-	-	-
Normal - Abnormal, clinically irrelevant	-	-	-	-	-
Normal - Abnormal, clinically relevant	-	-	-	-	-
Abnormal, clinically irrelevant - Normal	-	-	-	-	-
Abnormal, clinically irrelevant - Abnormal, clinically irrelevant	-	-	-	-	-
Abnormal, clinically irrelevant - Abnormal, clinically relevant	-	-	-	-	-
Abnormal, clinically relevant - Normal	-	-	-	-	-
Abnormal, clinically relevant - Abnormal, clinically relevant	-	-	-	-	-
Abnormal, clinically relevant - Abnormal, clinically irrelevant	-	-	-	-	-

**Table 26 – Coagulation – Safety population**

	Total (n=xx)				
	Screening	Baseline	Visit xx	End of study treatment	End of study
Prothrombin time, n (%)					
Normal					
Abnormal, clinically irrelevant					
Abnormal, clinically relevant					
Total					
Baseline versus current visit					
Normal - Normal	-	-	-	-	-
Normal - Abnormal, clinically irrelevant	-	-	-	-	-
Normal - Abnormal, clinically relevant	-	-	-	-	-
Abnormal, clinically irrelevant - Normal	-	-	-	-	-
Abnormal, clinically irrelevant - Abnormal, clinically irrelevant	-	-	-	-	-
Abnormal, clinically irrelevant - Abnormal, clinically relevant	-	-	-	-	-
Abnormal, clinically relevant - Normal	-	-	-	-	-
Abnormal, clinically relevant - Abnormal, clinically relevant	-	-	-	-	-
Abnormal, clinically relevant - Abnormal, clinically irrelevant	-	-	-	-	-
APTT, n (%)					
Normal					
Abnormal, clinically irrelevant					
Abnormal, clinically relevant					
Total					
Baseline versus current visit					
Normal - Normal	-	-	-	-	-
Normal - Abnormal, clinically irrelevant	-	-	-	-	-
Normal - Abnormal, clinically relevant	-	-	-	-	-
Abnormal, clinically irrelevant - Normal	-	-	-	-	-
Abnormal, clinically irrelevant - Abnormal, clinically irrelevant	-	-	-	-	-
Abnormal, clinically irrelevant - Abnormal, clinically relevant	-	-	-	-	-
Abnormal, clinically relevant - Normal	-	-	-	-	-
Abnormal, clinically relevant - Abnormal, clinically relevant	-	-	-	-	-
Abnormal, clinically relevant - Abnormal, clinically irrelevant	-	-	-	-	-
INR, n (%)					
Normal					
Abnormal, clinically irrelevant					
Abnormal, clinically relevant					
Total					

**Table 26 (Cont.) – Coagulation – Safety population**

	Total (n=xx)				
	Screening	Baseline	Visit xx	End of study treatment	End of study
INR, n (%)					
Normal					
Abnormal, clinically irrelevant					
Abnormal, clinically relevant					
Total					
Baseline versus current visit					
Normal - Normal	-	-	-	-	-
Normal - Abnormal, clinically irrelevant	-	-	-	-	-
Normal - Abnormal, clinically relevant	-	-	-	-	-
Abnormal, clinically irrelevant - Normal	-	-	-	-	-
Abnormal, clinically irrelevant - Abnormal, clinically irrelevant	-	-	-	-	-
Abnormal, clinically irrelevant - Abnormal, clinically relevant	-	-	-	-	-
Abnormal, clinically relevant - Normal	-	-	-	-	-
Abnormal, clinically relevant - Abnormal, clinically relevant	-	-	-	-	-
Abnormal, clinically relevant - Abnormal, clinically irrelevant	-	-	-	-	-

